3. DESCRIPTION OF THE INVESTIGATIONAL DEVICE

 is a continuous, scalable, patient-worn, vital signs monitor , which provides the versatility of a bedside monitor in a wearable device.

 monitors a wide range of physiological parameters. Designed to scale up or down with patient acuity,  combines the reliability and accuracy of a bedside monitor with the comfort and freedom of a wearable device, allowing for ambulation and movement during continuous monitoring. Suitable for use across the continuum of care,  offers advanced flexibility and is easily scalable to accommodate surges in patient volume and each patient's level of acuity.

The focus of this study is on the validation of the mean arterial pressure (MAP) parameter of Masimo INVSENSOR00073. Masimo INVSENSOR00073 provides systolic, diastolic, and mean arterial blood pressure readings through an oscillometric method. An oscillometric method of blood pressure measurement is a noninvasive method that monitors the amplitude of cuff pressure changes during cuff deflation to determine arterial blood pressure. Masimo INVSENSOR00073 consists of a reusable module and a disposable cuff, which plug into the  device, or a laptop for data collection purposes.

For blood pressure measurements, the cuff is wrapped around the non-dominant arm, making sure that the cuff's Artery Marker is aligned over the brachial artery. To locate the brachial artery, one should place the pads of his/her index and middle fingers halfway between the shoulder and elbow, in the middle of the inner arm, between the biceps and triceps muscles. The cuff should fit comfortably around the patient's arm for maximum oscillometric signal quality. The lower edge of the cuff should be located 2 cm above the antecubital fossa (interior bend of the elbow).

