7.6.2.2. Health Assessment and Eligibility Determination

After informed consent, subjects will be screened to determine eligibility for study enrollment and safe participation in the study. Subjects must meet all inclusion criteria and none of the exclusion criteria to participate in the study. All subjects screened will be documented on the *Screening and Enrollment Log*. Subjects who do not meet the eligibility criteria will be considered screen failures and the reason for the status of screen failure will be documented on the *Screening and Enrollment Log*.

Information on subject demographics (including but not limited to sex, race and ethnicity, skin pigmentation, age, height, and weight), arms circumference, and a medical history may be collected.

- Pregnancy Screening:

Female subjects will be required to take a pregnancy test. Subjects will be notified of their pregnancy result and the result will be noted. Subjects will be excluded from the study if the result is positive.

- Vital Signs Screening:

Vital signs such as blood pressure, heart rate, and pulse oximetry measurements such as SpO₂, SpCO, and SpHb may be checked and recorded for subject safety monitoring.

Transient increases in blood pressure and heart rate can be expected during line placement, needle sticks, blood draw, etc. and may also be attributed to anxiety/nervousness relating to a new environment. For most participants, only the initial recorded blood pressure and/or heart rate determines a subject's qualification for the study. In the case where heart rate and blood pressure changes suggest participant discomfort or a potential safety concern, the participant will be removed from the study after qualifying, according to the discretion of medical and study staff.

Assessment of lateral difference in blood pressure measurements between the left and right arms will be done with simultaneous blood pressure reading in both arms. Simultaneous blood pressure reading in both arms will be performed using FDA-cleared auscultatory measure three times, following best practices (e.g., positioning the middle of the cuff on the patient's upper arm at the level of the right atrium [the midpoint of the sternum]). Study will only proceed if the lateral difference is ≤ 15 mmHg for the systolic blood pressure (SBP), and ≤ 10 mmHg for the diastolic blood pressure (DBP). Otherwise, the subject will be withdrawn from participating in the study.

- Venous and Arterial Access Screening:

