8.2.1. Accuracy Calculations

Mean error and standard deviation for the MAP measurements from the Masimo INVSENSOR00073 device under investigation in comparison with measurements from the reference invasive radial arterial line (A-line) will be calculated.

Since the opposite limb is used for reference site of intra-arterial blood pressure recording, the results shall be corrected for the lateral difference. The lateral difference will be calculated as the average difference between the reference readings or determinations made on each limb according to the formula (1) below:

$$(1) \text{ Lateral Difference: } LD = \frac{1}{3} \times (\sum_{i=1}^3 p_i - \sum_{j=1}^3 p_j),$$

Where i is the index for the determination on the limb used for the sphygmomanometer-under-test determination, and j is the index for the reading on the limb used for the reference reading.

Lateral difference will be calculated for each subject prior to taking invasive measurements, using two identical automated sphygmomanometers. If the lateral difference of the reference systolic blood pressure is > 15 mmHg or the lateral difference of the reference diastolic blood pressure is > 10 mm Hg, subject will not participate in the study.

For those who are eligible to participate in the invasive measurement, sphygmomanometer-under-test error, x , is calculated by taking the difference between the sphygmomanometer-under-test blood pressure and the reference blood pressure and by adding the lateral difference (LD) if the sphygmomanometer-under-test blood pressure was taken in the left arm, according to formula (2), or subtracting LD if the sphygmomanometer-under-test blood pressure was taken in the right arm, according to formula (3).

$$(2) \text{ Sphygmomanometer-under-test error (worn on left arm), } x = p_{SUT_L} - p_{REF_R} + LD,$$
$$(3) \text{ Sphygmomanometer-under-test error (worn on right arm), } x = p_{SUT_R} - p_{REF_L} - LD,$$

Where p_{SUT_L} and p_{SUT_R} are sphygmomanometer-under-test blood pressures in the left (L) and right (R) arms, respectively; and similarly, p_{REF_L} and p_{REF_R} are reference blood pressures in the left (L) and right (R) arms, respectively.

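### Formula (2) adds a lateral difference that formula (1) defines as test limb minus reference limb, so left-arm cuff readings have the arm offset doubled instead of removed

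*Combined protocol and SAP*

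**What the plan says.** Section 7.6.3.2 puts the test cuff on the arm opposite the arterial line, so every paired reading contains any pressure difference between the arms. Section 8.2.1 sets out to correct for it.

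- **Formula (1)** is the mean of three readings indexed i minus the mean of three indexed j. The text explains that "i is the index for the determination on the limb used for the sphygmomanometer-under-test determination" and that "j is the index for the reading on the limb used for the reference reading". LD is therefore cuff limb minus reference limb, whichever arm wears the cuff.
- **Formula (2)**, cuff on the left, is "x = p_{SUT_L} - p_{REF_R} + LD". The prose gives the same rule, forming the error "by adding the lateral difference (LD) if the sphygmomanometer-under-test blood pressure was taken in the left arm", so the plus sign is not a misprint or a fault of text extraction.
- **Formula (3)**, cuff on the right, subtracts LD.

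On which arm is used, section 3 says "the cuff is wrapped around the non-dominant arm".

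On how LD is measured, section 7.6.2.2 says "Simultaneous blood pressure reading in both arms will be performed using FDA-cleared auscultatory measure three times", and section 7.5.1 also refers to auscultatory values. Section 8.2.1 says LD is obtained "using two identical automated sphygmomanometers". Systolic and diastolic pressures are named in the eligibility limits for LD (15 and 10 mmHg), but the pressure p in formula (1) is not identified.

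The corrected errors feed formulas (4) and (5), the mean and SD, which section 8.2.2 judges against 5 and 8 mmHg.

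**The concern.** A correction whose sign changes with the arm makes sense only if the quantity being added or subtracted has a fixed left/right orientation. Formula (1) gives LD a test/reference orientation, which already reverses when the cuff changes arm. Reversing the sign again in formula (2) undoes the correction and adds the offset a second time.

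The study has one endpoint, MAP accuracy, and one pass/fail rule, and both rest entirely on these errors. A wrong sign can fail an accurate device by widening the SD, or pass a biased one if the average arm difference offsets the bias. If the mismatch is noticed only once data are in hand, the sign would be chosen with the result in view.

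A related gap lies in the same correction. The analyst needs an LD for MAP, but the plan does not say that p is MAP, and its two accounts of the measurement disagree. Auscultation gives systolic and diastolic values and no direct MAP.

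**Working it through.** **Algebra.** Let L and R be the true MAP in the left and right arms and e the device error. The aim is x = e.

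- Cuff left, line right: formula (1) gives LD = L − R. Formula (2) gives x = (L + e) − R + (L − R) = e + 2(L − R).
- Cuff right, line left: formula (1) gives LD = R − L. Formula (3) gives x = (R + e) − L − (R − L) = e.

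The right-arm rule removes the offset; the left-arm rule doubles it.

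**Numbers, perfect device (e = 0), cuff on the left**

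| Left MAP | Right MAP | LD by (1) | Uncorrected | Formula (2) | Correct |
|---|---|---|---|---|---|
| 100 | 94 | +6 | +6 | +12 | 0 |
| 95 | 90 | +5 | +5 | +10 | 0 |
| 90 | 95 | −5 | −5 | −10 | 0 |

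**Largest eligible case.** With LD of 15 systolic and 10 diastolic, and MAP taken as DBP + (SBP − DBP)/3 (an assumption), the MAP offset is 10 + (15 − 10)/3 = 11.7 mmHg. Formula (2) then gives a spurious error of 2 × 11.7 = 23.3 mmHg for that subject.

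**Effect on the reported SD.** The documents give no distribution for LD, no expected error SD and no handedness, so these are assumed. Let f be the share of left-arm cuffs, and let LD have mean 0 and be independent of device error. Then SD as written = √(SD_true² + f × 4 × SD_LD²). With SD_true = 6 and f = 0.9:

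- SD_LD = 2: √(36 + 14.4) = 7.1
- SD_LD = 3: √(36 + 32.4) = 8.3
- SD_LD = 4: √(36 + 57.6) = 9.7

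The limit of 8 is crossed when 3.6 × SD_LD² = 64 − 36 = 28, that is at SD_LD = 2.8.

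**Effect on the mean.** A left-cuff LD averaging +2 mmHg shifts the mean error by 0.9 × 2 × 2 = +3.6. An average of +3 shifts it by 0.9 × 2 × 3 = +5.4, beyond the limit of 5.

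**Chance of passing, by simulation.** 20 subjects with 8 readings each, mean LD 0, no device bias, LD measured without error; pass means absolute mean error at most 5 and SD at most 8. For a true error SD of 6, the within-subject SD is 5 and the between-subject SD 3.3; other error SDs keep the same ratio. With the correct sign the chance is 1.00 in every row.

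| True error SD | Left-arm share | SD_LD 1 | SD_LD 2 | SD_LD 3 | SD_LD 4 |
|---|---|---|---|---|---|
| 6 | 90% | 1.00 | 0.93 | 0.48 | 0.12 |
| 6 | 50% | 1.00 | 0.99 | 0.83 | 0.51 |
| 5 | 90% | 1.00 | 1.00 | 0.75 | 0.25 |
| 4 | 90% | 1.00 | 1.00 | 0.90 | 0.41 |

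For comparison, with no correction at all the first row would be 1.00, 1.00, 0.99 and 0.91.

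**False pass.** With a true bias of −7 mmHg, mean LD +2, SD_LD 2, error SD 6 and 90% left cuffs, the correct formula passes about 1% of studies and the formulas as written about 82%, because the mean moves to −7 + 3.6 = −3.4.

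**The case against.** The strongest reply is that the slip may lie in the definition of i and j, with the signs as intended. The prose rule and formulas (2) and (3) agree with one another if LD is always right minus left, and an analyst who computed it that way would get correct errors. This stands as a point about where the mistake was made: the documents establish a contradiction between (1) and (2) and cannot show which was meant. It does not rescue the text, because nothing in it gives LD a right-minus-left orientation, and literal application gives wrong values.

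Other points also have weight.

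- Left-arm predominance is an inference. Section 3 names the non-dominant arm, while section 7.6.3.2 requires only the arm opposite the line, and handedness is not recorded in the plan.
- The size depends on assumed inputs. With SD_LD of 1, or a smaller device error together with SD_LD of 2, the effect on passing is negligible.
- The SD is inflated only if LD or the cuff side varies between subjects. That claim, and the comparison with no correction, assume LD is not negatively related to device error.
- The 23 mmHg figure is one extreme subject's error, whereas the limits of 5 and 8 apply to a mean and SD over at least 150 readings, so the two are not directly comparable.
- Section 8.2.1 opens with MAP, so reading p as MAP is natural. The fair criticism is that the plan does not say so.
- The auscultatory/automated conflict is a separate fault with its own fix and adds nothing to the sign error.

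**Conclusion.** The concern holds. Formulas (1) and (2), taken together as written, give x = e + 2 × LD for every left-arm cuff reading; the value is wrong whenever LD is not zero. Formula (3) is consistent with (1). No other section resolves the mismatch, and it enters the study's only acceptance test directly.

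The sign error rests on no assumption; its practical size does. With SD_LD of 2 to 4 mmHg and mostly left-arm cuffs, an accurate device's chance of passing ranges from essentially unaffected to 0.12 across the error SDs examined (4 to 6 mmHg). At an error SD of 6, formula (2) does worse than leaving the readings uncorrected. An average arm difference away from zero can also hide a real bias of the opposite sign. This must be corrected before any data are analysed.

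**What to change.** Choose one of two equivalent changes in section 8.2.1:

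1. Keep formula (1) and replace (2) and (3) with a single formula for both arms, x = pSUT − pREF − LD, amending the prose to match.
2. Redefine LD in formula (1) as right arm minus left arm for every subject, and keep (2) and (3).

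Check of each with left 95, right 90, e = 0 and the cuff on the left: option 1 gives 95 − 90 − 5 = 0; option 2 gives 95 − 90 + (90 − 95) = 0.

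State also that p in formula (1) is MAP, taken from the two automated devices already named in section 8.2.1, or computed as DBP + (SBP − DBP)/3 if they do not display MAP. Make the synopsis and sections 7.5.1 and 7.6.2.2 agree with section 8.2.1 on the method. Check the analysis program against the corrected formula with one worked example for each arm.

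The cost is rewording the formulas and the screening text through an amendment. No subjects or procedures are added.

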7.6.3.2. Cuff Placement and Measurement

Masimo INVSENSOR00073 cuff shall be placed on the opposite limb from the arterial line. Care should be taken to ensure that both the arterial line transducer and Masimo INVSENSOR00073 cuff are at the level of the participant's left ventricle of the heart. Data collection software(s) will be set up for data acquisition.

[figure not shown]

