Controlled Hypotension		

Table 3. Minimum and Maximum blood pressure levels

[figure not shown]
Blood Pressure	Minimum (mmHg)	Maximum (mmHg)
Systolic Blood Pressure		
Diastolic Blood Pressure		

Study Title: Validation Study of Mean Arterial Pressure (MAP) Parameter of Masimo
INVSENSOR00073

Revision: 

Mean Arterial Pressure (MAP)  

[figure not shown]
Medication Preparation and Administration

Primary and safety drugs will be prepared for each subject prior to beginning the blood pressure variation procedures. A trained clinician will prepare all infusions containing the primary drug. 

[figure not shown]
Only full and unused syringes will be used for each subject. Partially used syringes will be discarded after each subject completes the study.

Infusion rates for each titration step are calculated by the medication infusion pump based on the subject's weight  and the drug concentration. 

 Two independent clinicians must verify medication pump settings before changing the current setting.

If the subject participates in the induced hypertension procedure (increased blood pressure), the infusion with  will be given at a starting dose of  µg/kg/min. 

If the subject participates in the induced hypotension procedure (decreased blood pressure), the infusion with  will be given at a starting dose of  µg/kg/min. 

After gauging subject response to the initial infusion, the drug will be titrated to achieve the desired blood pressure variation. Dose increases may continue to titrate up to the targeted blood pressure change as long as the subject remains 

[figure not shown]
Study Title: Validation Study of Mean Arterial Pressure (MAP) Parameter of Masimo
INVSENSOR00073

Revision: 

asymptomatic and the dose does not exceed the maximum of  µg/kg/min. See Table 4 for the  and  dose schedules.

Table 4. Dose schedule for  and 

Drug	Starting Dose (µg/kg/min)	Step Size/Schedule (µg/kg/min)	Maximum Dose (µg/kg/min)	Dose Increase Wait Time
				
				

Primary drug infusion stops when the target blood pressure change is maintained for the period of time  the subject develops symptoms, blood pressure limits are reached/exceeded, or the total drug infusion time per  After primary drug infusion ceases, the subject's blood pressure is allowed to passively return to baseline. Baseline is considered achieved when the subject's blood pressure is within 10 mmHg of their initial blood pressure levels.

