The reference MAP will be read from the values displayed on the reference invasive blood pressure monitoring equipment. Since the recording is not interrupted due to cuff inflation, the reference blood pressure ranges shall be determined from the recording of the invasive blood pressure for a duration of at least 30 seconds that includes the period of determination of INVSENSOR00073. Specifically, 30 seconds of reference recordings prior to the determination of INVSENSOR00073 will be used. Reference recordings and determination of Masimo INVSENSOR00073 will be synchronized based on the time stamp of the data acquisition device.

For the sphygmomanometer-under-test, the mean value of the errors \bar{x}_n and experimental standard deviation s_n of the n individual paired determinations of the Masimo INVSENSOR00073 for all subjects shall be calculated according to the formulas (4) and (5) below:

$$(4) \text{ Mean Error: } \bar{x}_n = \frac{1}{n} \times \sum_{i=1}^n x_i$$

$$(5) \text{ Standard Deviation: } s_n = \sqrt{\frac{1}{n-1} \times \sum_{i=1}^n (x_i - \bar{x}_n)^2},$$

where x_i is the error of the i^{th} individual determination, n is the total number of determinations, and i is the index for the individual determination.

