8.2.3. Data Exclusion Criteria

The following data exclusion criteria will be applied before statistical analysis.

- Either reference or test device malfunctions and/or provides inconsistent values or not values.
- Discontinuities and abrupt dropouts due to device failure.
- Any invasive systolic blood pressure change greater than [REDACTED], or diastolic blood pressure changes greater than [REDACTED] during or before determination by the sphygmomanometer-under-test.
[REDACTED] Diastolic blood pressure outside of the Masimo INVSENSOR00073 specifications of [REDACTED]
- Systolic blood pressure outside of the Masimo INVSENSOR00073 specifications of [REDACTED]

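### Section 8.2.1 gives two reference-pressure windows that conflict if read literally, and does not say which event the synchronising time stamp marks

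*Combined protocol and SAP*

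**What the plan says.** Section 8.2.1 (Accuracy Calculations) describes the reference in four consecutive statements.

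- Source: "The reference MAP will be read from the values displayed on the reference invasive blood pressure monitoring equipment".
- First window: because cuff inflation does not interrupt the recording, the reference is determined from the invasive trace "for a duration of at least 30 seconds that includes the period of determination of INVSENSOR00073".
- Second window: "Specifically, 30 seconds of reference recordings prior to the determination of INVSENSOR00073 will be used".
- Alignment: "Reference recordings and determination of Masimo INVSENSOR00073 will be synchronized based on the time stamp of the data acquisition device".

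Three other sections bear on the point. Section 7.6.3.2 says the "cuff shall be placed on the opposite limb from the arterial line", which is why inflation leaves the arterial trace intact. Section 8.2.2 sets the limits: mean error 5 mmHg and SD 8 mmHg. Section 8.2.3 excludes readings with too large a change in invasive systolic or diastolic pressure "during or before determination by the sphygmomanometer-under-test"; the size of that change is redacted.

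**The concern.** The second window is introduced as the detail of the first, yet on its plain wording it breaks the first one's condition. A window lying wholly before the determination cannot include it. The reason given for the first window, an uninterrupted trace on the other arm, is a reason to measure both arms at the same time.

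Every error in formulas (2) and (3) is the device value minus a reference value, adjusted for the lateral difference. If the reference is taken earlier than the device reading, any pressure change in between is counted as device error: positive when pressure is rising, negative when it is falling. Drift in both directions inflates the SD; drift mostly in one direction moves the mean.

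This study moves pressure on purpose. Under section 7.6.3.3 the drug is titrated towards a target and pressure then returns passively to baseline. The readable text does not confine readings to the plateau. Because the choice of window is open, it could also be made after the data have been seen.

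**Working it through.** The plan has no figure of its own to reproduce here. It supplies the two windows, the error formulas and the limits of 5 and 8 mmHg. The rest is assumed:

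- determination time T = 20, 30 or 40 s;
- linear MAP drift r = 2, 5 or 10 mmHg/min;
- device MAP representing pressure at the midpoint of the determination;
- a share f of retained readings taken during drift;
- an SD without artefact of SD0, with drift independent of the device's own error.

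**1. Coverage.** Let the determination run from 0 to T seconds.

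- Literal reading: the window runs from −30 to 0 and covers 0% of the determination for every T.
- Alternative reading (30 s ending at the displayed result): the window runs from T − 30 to T and covers min(30, T)/T. That is 100% at 20 and 30 s but 30/40 = 75% at 40 s, where the first 10 s are missed.

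**2. Lag and artefact.** The lag is the device midpoint T/2 minus the window centre. The centre is −15 on the literal reading and T − 15 on the alternative. So the lag is 15 + T/2 (literal) or 15 − T/2 (alternative), and the artefact is b = r × lag/60.

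| T (s) | Literal lag (s) | b at 2 / 5 / 10 mmHg/min | Alternative lag (s) | Size of b at 2 / 5 / 10 |
|---|---|---|---|---|
| 20 | 25 | 0.8 / 2.1 / 4.2 | +5 | 0.2 / 0.4 / 0.8 |
| 30 | 30 | 1.0 / 2.5 / 5.0 | 0 | 0 / 0 / 0 |
| 40 | 35 | 1.2 / 2.9 / 5.8 | −5 | 0.2 / 0.4 / 0.8 |

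The two readings place the window T seconds apart. At 10 mmHg/min the same trace therefore gives reference values differing by 10 × 30/60 = 5.0 mmHg at T = 30 s, or 6.7 mmHg at T = 40 s. On a steady plateau both give the same value.

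**3. SD, literal reading, rises and falls balanced.** SD = √(SD0² + f·b²).

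| SD0, f | 10 mmHg/min, T = 20 / 30 / 40 s | Largest value at 5 mmHg/min |
|---|---|---|
| 7.5, 30% | 7.84 / 7.98 / 8.15 | 7.67 |
| 7.0, 60% | 7.71 / 8.00 / 8.33 | 7.36 |

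Example: √(7.5² + 0.3 × 5.83²) = √66.46 = 8.15. The limit is exceeded only at T = 40 s and 10 mmHg/min.

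**4. Mean, literal reading, drift all one way.** Shift = f·b. At 10 mmHg/min this is 1.25 to 1.75 mmHg for f = 30% and 2.5 to 3.5 mmHg for f = 60%. Neither reaches 5 mmHg unless the device is already biased.

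**5. Threshold.** The MAP change over the 30 s window plus the determination is D = r(30 + T)/60. Since b = r(15 + T/2)/60, b = D/2 whatever T is. The SD reaches 8 when b = √((64 − SD0²)/f).

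- SD0 = 7.5, f = 0.3: √(7.75/0.3) = 5.08, so D = 10.2 mmHg.
- SD0 = 7.0, f = 0.6: √(15/0.6) = 5.00, so D = 10.0 mmHg.

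Both exceedances in step 3 need MAP to move 10 × 70/60 = 11.7 mmHg in 70 s.

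**The case against.** The best defence is that the two sentences can be reconciled. Elsewhere in section 8.2.1 a determination is often the value obtained rather than the interval, and the first window sentence uses a separate phrase for the interval. Thirty seconds ending at the output value would then satisfy both sentences, with an artefact of at most 0.8 mmHg even at 10 mmHg/min. This reading is plausible but not established: section 8.2.3 uses the same word for an interval, the stamped event is not stated, and the reconciliation fails beyond 30 s.

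The effect is also limited. The infusion rule, "Primary drug infusion stops when the target blood pressure change is maintained for the period of time", implies a plateau, where the artefact is near zero. The stability exclusion removes large changes, and nothing in the documents shows that the two cases above 8.0 would survive it. This stands, and it keeps the point modest. But the exclusion neither chooses a window nor defines the stamp. Its limits are for systolic and diastolic pressure, so comparing them with a MAP change of about 10 mmHg is indirect. The half-of-D result also rests on the midpoint assumption.

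Two smaller points are fair. The first window sentence speaks of ranges of reference pressure rather than naming MAP, although in context it describes the reference for the MAP error. Stamp timing could appear in material not readable here, such as the figure in section 7.6.3.2 or the Appendix I workflow, so the omission is confirmed only for the readable text. Neither removes the conflict within section 8.2.1.

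**Conclusion.** The concern holds. Read literally, section 8.2.1 prescribes a reference window that breaks its own requirement, and the readable text does not settle which window is meant. It should be corrected before analysis because it governs the reference value in every paired error.

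Confidence is high on the conflict in the text and lower on its consequence. Drift rate, determination time, share of drifting readings and underlying SD are all assumed. Under those assumptions the literal window adds from nothing to about 5.8 mmHg to a single reading. It carries the SD past 8 mmHg only when the underlying SD is already 7.0 to 7.5 and MAP moves by more than about 10 mmHg across the window and determination in 30% to 60% of retained readings. A device well inside both limits would pass either way.

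**What to change.** Replace the second window sentence in section 8.2.1 with one rule that meets the first:

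- The reference MAP is the average of the recorded arterial MAP over a window of at least 30 s that contains the whole determination, lengthened when a determination exceeds 30 s.
- The window's start and end are fixed relative to a named device event. For determinations shorter than 30 s, state where the window sits; centring it on the determination would remove the remaining lag.
- State whether the time stamp marks the start of inflation or the displayed result.

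Report mean error and SD with the preceding 30 s window as a sensitivity analysis. If the sponsor did mean 30 s ending at the displayed result, the text should say so and cover determinations longer than 30 s. The sponsor can also check the unredacted limits in section 8.2.3 against the MAP change of about 10 mmHg derived above, allowing for their being systolic and diastolic limits.

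The cost is a wording amendment under section 10 and one change to the data-extraction script. The plan already provides for a time-stamped arterial recording, so no further data or subject exposure is needed.
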